## 1. List of Abbreviations

Abbreviation	Abbreviation definition
FN	Family Navigation
FP	Family Partners
ACO	Accountable Care Organization
MOST	Multiphase Optimization Strategy
OCHIN	Oregon Community Health Information Network
CCM	Chronic Care Model
PPSC	Preschool Pediatric Symptom Checklist
PSC-17	Pediatric Symptom Checklist-17
SWYC	The Survey of Wellbeing of Young Children
CBCL	Child Behavior Checklist
PSN-I	Interpersonal Relationship with Navigator
PHQ-2	Patient Health Questionnaire
FRS	Family Resource Scale
EHR	Electronic Health Record
RE-AIM	Reach Effectiveness Adoption Implementation Maintenance
TAU	Treatment as Usual

## 2. Protocol Summary

Title:	Optimizing a Paraprofessional, Family Partner Navigation Model for Children
Population:	The study will include 715 participants which include parent/legal guardian, a child and eligible siblings who will be enrolled from DotHouse Health, a Federally Qualified Community Health Center in Boston. We will enroll children ages 3-12 years who screen positive on behavioral health screening tools, - the Preschool Pediatric Symptom Checklist (PPSC) (3-5 years), which is included in the Survey of Wellbeing of Young Children (SWYC) or Pediatric Symptom Checklist-17 (PSC-17) (6-12 years) OR whose parents indicate a behavioral health concern during any pediatric visit. These screening tools are administered as standard of care (SOC). The study enrollment is expected to be 84% ethnic-racial minority families (i.e. primarily Asian, Latino, and African American).
Intervention:	This is a pragmatic optimization trial of Family Navigation (FN), an evidence-based care management strategy which is a promising intervention to help low income and minority families access timely mental health services. Despite significant evidence supporting the effectiveness of FN, concerns exist about the ability to disseminate FN to a broad population due to inefficiency and cost. The current proposal is designed to develop an optimized, efficient, effective, and equitable version of FN to be delivered by trained Family Partners (FP), the goal being to improve access to, and engagement in, diagnostic and treatment services for children with mental health disorders. Specifically, families who participate in the study (includes parent/legal guardian, child and if applicable, additional siblings) will work with one of the trained study Family Partners (FPs) and will be randomized to one of 16 possible strategies to

	deliver FN. FPs will then work with families based on the condition to which they were randomized.
Objectives:	Our primary objective is to identify which of the FN delivery strategies: (A) use of enhanced technology for care coordination vs. usual care; (B) community and home-based delivery vs. clinic-based delivery only; (C) intensive symptom tracking vs. low level symptom tracking; and (d) individually tailored vs standardized, schedule-based visits with families contribute meaningfully to improvement in the primary outcome - access to child mental health services. We will estimate impact of the 4 delivery strategies and the combinations of these strategies on the study's primary outcome. Based on our findings we will determine the best combination of FN components for evaluation in future randomized trial. Our secondary objectives are to evaluate which components of FN are most effective for whom and the mechanisms related to effectiveness.
Design/Methodology:	
We will be using a highly efficient experimental design to identify which of the FN components contribute meaningfully to improvement in the primary outcome - access to child mental health services. We will concurrently gather information on FN's mechanisms of effectiveness. The study will take place in the real world context of a community health care center.
 
Children will be enrolled if they have a positive behavioral health screen on one of the age appropriate screening measures (PSC or PPSC) which are universally used in the clinic OR parent report of a behavioral health concern. If agreeable, families will be referred to a FP who will inform families about the study. Families who consent to study participation will be randomized to one of 16 combinations of strategies to deliver FN and will work with the study FP. Families who decline participation in the study will have the option to work with health center care managers (instead of the study FPs) who also offer care coordination. Those families will not be randomized or followed as part of the study.
 
Delivery of FN will be systematically varied across four components, each of which is represented by a separate factor in our 2x2x2x2 factorial study design (See figure 1). Specifically, each family (includes parent/legal guardian, child and if applicable, additional siblings) will be randomly assigned to one of two conditions within each of 4 factors or delivery strategies, defining 16 separate experimental conditions. Strategies include: (A) technology-assisted delivery of care coordination using an innovative, web-based platform called Act.MD (compared to usual care); (B) clinic based FN + community-based (compared to clinic-based only); (C) enhanced symptom tracking using more frequent behavioral symptom tracking by the FP (compared to standard pediatric surveillance); and (d) individually tailored vs standardized, schedule-based visits with families. All children will be followed through the EHR for 12 months, for outcomes in services access and symptom tracking.

We will estimate main effects of the 4 experimental factors and the effects of combinations of the delivery strategies on the study's primary outcome – family engagement in child mental health services.

We will also include a “watchful waiting” group for families of children who are referred to the study but who decide that they are not interested in accessing child behavioral services when the FP speaks to them about study enrollment. The FP will ask parents if she can reach out to them in 3 months to see if they desire services for the child at that time. If upon recontacting the family, they would like services and would like to work with the FP, the family will have the opportunity to enroll in the study and be randomized to a study condition.

Total Study Duration:	4.5 years ( 6 month start up period)
Subject Participation Duration:	12 months

### 3. Background/Rationale & Purpose

#### 3.1 Background Information

**Description of the health issue and research question.** Significant disparities exist in access to mental health services for low income and ethnically diverse children. On average, low income and minority children are diagnosed later than their white, higher income peers, and experience substantial delays in initiating treatment – even after diagnosis. Obtaining a diagnosis and engaging with treatment involves a number of complex steps, including: visits to primary care for screening, visits to a subspecialist for diagnosis, receipt of an individually-tailored treatment plan, and ongoing specialty support. Common barriers include availability of services, miscommunication, complex payment systems, and cultural bias. In addition, because children require coordination of the entire family unit across many systems (school, medical, community), unique challenges (e.g., parent stress, parent-provider communication) also exist for this population. Therefore, an individually tailored intervention, based on principles of engagement in mental health and family dynamics, is necessary to alleviate disparities for this population.

**Research Question.** Which FN components contribute meaningfully to improvement in access to child mental health services, defined as engagement in mental health service within 90 days after randomization.

**Brief description of the study intervention: A paraprofessional model of family navigation for child behavioral health.** FN is an evidence-based care management strategy designed to reduce disparities in care, and thus, represents a promising strategy to help low income and minority families access timely mental health services. Traditional navigation models utilize trained community health workers who assist families in overcoming systems and patient-specific barriers to a defined set of services over a time-limited period. Navigators - in the proposed study called “Family Partners” (FPs) – are paraprofessionals who share key attributes (cultural, language, lived experience) with the population served. FN is rooted in the Chronic Care Model and has evidence in diseases such as cancer and HIV as a means to reduce disparities by shortening the interval between a positive screen (e.g., a mammogram for breast cancer) and definitive diagnosis. Data from our group and others demonstrate that a

paraprofessional model of FN can reduce the time from screening to diagnosis and improve access to, and retention in, treatment services for a variety of child mental health disorders.

**Delivery of family navigation: who, how, what, and why does it matter?** Despite the promise of FN to reduce disparities in access and engagement in services, studies demonstrate varying success or diminution of impact of FN upon implementation in real-world practice. These findings suggest that a set of fundamental questions about FN still need to be answered. FN is a complex, multi-component intervention that incorporates motivational interviewing (MI), problem-solving, patient education, and care coordination. Components can be delivered through a range of strategies, including: clinic-based meetings, home visits, telehealth, web technologies or mobile technologies. In this study, all participants will receive the same core FN intervention which will be delivered by one of two FPs. FPs will be trained in MI and problem solving techniques, child mental health conditions, community resources, and care coordination (see page 13 for a detailed description of core FN components). Families will be randomized to one of 16 combination of delivery strategies: Strategies include: (A) technology-assisted delivery of care coordination using an innovative, web-based platform called Act.MD that allows multiple users (parents, primary care clinicians, and schools, for example) to develop, communicate, and execute shared care plans (compared to usual care); (B) clinic based FN + community-based (compared to clinic-based only); (C) enhanced symptom tracking using more frequent behavioral symptom tracking by the FP (compared to standard pediatric surveillance) and (d) individually tailored vs standardized, schedule-based visits with families (see Figure 3).

Understanding how to best deliver FN, which delivery components are most critical (and for whom), and what strategy to employ for implementation is essential for future dissemination. FN delivery can be costly and time-consuming, even in the best of circumstances. Learning how to optimize FN by determining which components are most effective is critical to its scalability and sustainability—and ultimately its success as a public health intervention. At the same time, understanding FN's cost as well as who benefits most is critical to decisions about how to optimally deploy available resources and generate the most equitable benefit. Answering these questions is a necessary step toward creating an optimized version of FN, one that aligns with the "triple aim" of producing the greatest population impact at the lowest cost.

**Pertinent prior experience with the intervention.** From 2010 to 2017, our group implemented and tested multiple comprehensive care management systems for urban children and families with behavioral and mental health concerns (e.g., ADHD, ASD, maternal depression). These studies used rigorous designs (e.g., comparative effectiveness, hybrid implementation-effectiveness) to test paraprofessional interventions (e.g., navigators, care managers) to assist patients beginning at the earliest detection of risk. Families were navigated from primary care, early intervention, and Head Start to specialty behavioral and developmental services. The goals of these intervention studies were to address person and systems-level barriers to accessing services among low income and minority children, and are similar to those of the proposed study (albeit targeted to a different condition). For example, in an NIMH R21, Drs. [name] and [name] piloted FN to help mothers with depression access mental healthcare. In an NIMH R01, Drs. [name] and [name] are conducting a hybrid implementation-effectiveness trial of FN to enhance access to services for children who screened positive for ASD in primary care. [name] is currently directing TEAM UP, a multi-site pediatric behavioral health integration project in three federally qualified community health centers utilizing paraprofessional community health workers to improve engagement in services. These examples demonstrate the team's success in developing and testing strategies to improve early identification, treatment, and engagement for young children with behavioral concerns.

**Importance of the study.** Health service delivery reforms focused on primary care transformation - where primary care networks are promoted as the 'hub' of care coordination – are growing, and

financial incentives created under the Affordable Care Act are spawning new systems that link primary care and specialty services within integrated networks. For example, Accountable Care Organizations (ACOs) are groups of doctors, hospitals, and other healthcare providers, who join together to give coordinated, high quality care. Developing Family Navigation (FN) within the setting of a newly formed ACO (Boston Accountable Care Organization) links this innovation to the broader policy context and maximizes scale-up potential within emerging delivery systems. Understanding implementation within this new context is critical to FN's ultimate success as a public health intervention and effectively and efficiently assisting families in accessing behavioral health interventions..

**Known risks and potential benefits.** The proposed study offers minimal risk. It has the potential to assist participating families with access to child behavioral health services. The primary risk is breach of confidentiality; therefore, we have planned for protections of confidentiality throughout study procedures.

**This study will be conducted in compliance with the protocol, applicable regulatory requirements, and BMC/ BU Medical Campus Human Research Protection policies and procedures.**

### 3.2 Rationale and Purpose

**Importance and value of the information to be gained.** Despite significant evidence supporting the effectiveness of FN, concerns exist about the ability to disseminate this intervention to a broad population due to inefficiency and cost. The current proposal is designed to test which FN components are most efficient and effective. This information then guides assembly of an optimized FN model, tailored to low income and racial-ethnic minority families, seen in primary care and in accessing mental health services that achieves the primary outcomes with least resource consumption and participant burden .

**Innovating FN delivery through new methods and technologies.** Our principal innovation involves use of a Multiphase Optimization Strategy (MOST) to identify the most effective FN delivery approaches. Although FN has been previously used successfully across a variety of mental and behavioral health conditions (e.g., ASD and ADHD), we are proposing to use a methodology—one that is conceptually rooted in engineering and that emphasizes efficiency and careful management of resources—to systematically study FN delivery and guide the development of an optimized intervention model of FN for child behavioral health services. At the same time, to promote future spread, we are deliberately testing FN within the Oregon Community Health Information Network (OCHIN), embedded in the HER, OCHIN is a healthcare innovation center designed to promote the dissemination of quality care for all. Use of these methodologies and technologies within the study population offers the opportunity to develop an optimized FN delivery strategy, grounded in empirical data, that can be disseminated and provide a solution for barriers to behavioral health care engagement for traditionally undeserved children and families.

## 4. Objectives

### 4.1 Study Objectives

**Primary Objective:** To identify which of the FN delivery strategies: (A) use of enhanced technology for care coordination vs. usual care; (B) community and home-based delivery vs. clinic-based delivery only; (C) intensive symptom tracking vs. low level symptom tracking; and (d) ) individually tailored vs standardized, schedule-based visits with families contribute meaningfully to improvement in the primary outcome - access to child mental health services.

**Secondary Objective:** To evaluate the mechanisms of FN effectiveness and for whom it is effective.

## 4.2 Study Outcome Measures (See Table 1)

### 4.2.1 Primary Outcome Measures

#### Objective 1: To identify the most effective strategy to deliver FN

**Our primary outcome measure is receipt of behavioral health services within 90 days (yes/no)** will be defined as first encounter with behavioral health services within 90 days of randomization obtained from the electronic health record including Family Partner's template documentation.

Related to this primary objective, we will evaluate *time-to-receipt of behavioral health services* defined as time from randomization to first behavioral health service encounter obtained from the electronic health record, including family partner's template documentation. Dates will be obtained from administrative and billing data (electronic health records) for services within DotHouse, and FP documentation for services outside the health center.

A second primary outcome includes change in child symptoms over time.

- Pediatric Symptom Checklist-17 (PSC-17). A 17-item psychosocial screen designed to recognize cognitive, emotional, and behavioral problems. Three subscale Internalizing, Attention, and Externalizing have specific cutoffs and provide additional guidance regarding need for further follow-up. PSC-17 is embedded in the Epic (electronic health record) as a self-scoring form. It is widely used and has been validated in diverse populations.
- The Survey of Wellbeing of Young Children (SWYC). The SWYC screens for cognitive, motor, language, and social-emotional development among children up to 5½ years of age. We will track behavioral symptoms using the SWYC's Preschool Pediatric Symptom Checklist (PPSC), an 18-item questionnaire that has demonstrated strong concurrent validity with the Child Behavior Checklist (CBCL) and parents' reports of socio-emotional diagnoses as well as acceptability in diverse populations. Translations are available in a range of languages and the SWYC is currently being incorporated into the Epic system used at DotHouse.

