**Table 1. Primary and Secondary Outcomes**

	Outcome	Description	Measurement Source	Timing
Primary	Time to services	Time from randomization to first behavioral health service encounter	Electronic health record including FP's template documentation	90 days
	Access to services	1 st encounter with behavioral health services within 90 days of randomization	Electronic health record including FP's template documentation	90 days
	Child symptoms	Score on PSC-17 and SWYC	Measures will be sent to families via Epic's mobile app MyChart or administered by Zoom/telephone in REDCap or sent to the parent by mail	Baseline 3, 6, 9, & 12 mo
Secondary	Retention in services	≥4 visits or resolution of service need for families receiving psychotherapeutic or psychopharmacological services	Electronic health record including FP's template documentation	90 days
	Patient Satisfaction	HCQ & PSN-I	Measures will be sent to families via Epic's mobile app MyChart or administered by Zoom/ telephone in REDCap or sent by mail	6 mo
	Qualitative Parent Interviews	Parent interviews to describe the effect of cultural and linguistic concordance between patients and FN.	Interview completed through Zoom/phone and audio recorded, stored in HIPPA compliant BOX drive.	6 mo
	Qualitative DotHouse Staff Interviews	DotHouse staff interviews to understand their perspective in the implementation of family navigation (work flow changes etc).	Interview completed through Zoom/phone and audio recorded, stored in HIPPA compliant BOX drive.	ongoing

Note: The PSC-17 is currently administered to children at pediatric well visits at DotHouse as part of usual care. Plans are to implement the SWYC in summer/fall of 2018. Both tools have been used extensively and research supports use for symptom monitoring.

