### **12.2 Sample Size Determination**

#### **Sample Size and Power.**

Of the three measures to operationalize engagement, we powered our study on the dichotomous variable “receipt of BH services within 90 days” - the most conservative estimate. We base our power calculation on the number needed to detect the smallest differences in primary outcomes that are of clinical importance. Our formative work with staff at DotHouse and other community health centers indicates that a relative risk of approximately 25% would be considered clinically significant. Therefore, if 60% of families in the core navigation condition engage in mental health services (estimates based on our prior work), to detect a 25% difference (i.e. 75% of families in any of the FN delivery conditions engage in services), and assuming 2-tailed tests and a type 1 error rate of 5%, approximately 304 participants are required to detect this effect (n=38 in each of 8 cells). Although 304 participants are required for our power analysis, we will be enrolling 715 human subjects which include 304 parent/legal guardian, 304 index children for primary analysis and around 107 siblings for families with more than one eligible child. Additional sibling analysis will be done to explore differences in service goals etc.

We expect strong effects of study mediators, in particular fidelity variables and variables that are central to our theoretical model, such as increased parent capacity. Following published guidance based on an empirical review, we estimate that our design will have at least 80% power to detect mediation effects where the paths from independent variable to mediator and from mediator to outcome are of at least small-to-medium effect (ES=.26). Given that our mediation analyses are designed to support decisions regarding intermediate outcomes to be tracked for quality control and assurance, effect sizes less than this magnitude are not considered to be clinically important. In contrast, analyses of patient-level treatment moderators are exploratory as we have no evidence to support hypotheses of any effect.

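### One primary outcome is defined and powered, but others are also labelled primary with no testing order, so the false-success chance per factor could be about 10–13% instead of 5%

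*Combined protocol and SAP*

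**What the plan says.** **One primary outcome.** Section 4.1 asks which delivery strategies "contribute meaningfully to improvement in the primary outcome - access to child mental health services". The Protocol Summary states the objective in the same terms. The research question in section 3.1 defines access as engagement within 90 days of randomization. Section 12.1 states hypotheses about access only. Section 12.2 says "we powered our study on the dichotomous variable" of receipt within 90 days.

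**More than one.** Section 4.2.1 first names 90-day receipt as the primary measure and describes time to receipt as related to that objective. It then states: "A second primary outcome includes change in child symptoms over time". Table 1 has three rows in its primary block: access, child symptoms and time to services ("Time from randomization to first behavioral health service encounter"). Section 3.2 speaks of primary outcomes in the plural.

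**Testing.** The only significance level in the plan is in section 12.2, "assuming 2-tailed tests and a type 1 error rate of 5" per cent, within the calculation for the binary access outcome. Section 12.3 fits a logistic model for receipt and then Cox models for time. It does not make one test conditional on another, divide the error rate, or name a model for change in child symptoms.

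**The concern.** The product of this trial is a decision about which components enter the optimized package for a later trial. With two or three outcomes called primary and no stated order, a component with no effect has more than one chance to look successful. It could be kept on an outcome that has no power calculation and, for symptoms, no planned analysis. The DSMB Charter (section 5) adds to the ambiguity, since it provides for interim analyses of the primary end point without saying which one.

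This point concerns several outcomes within one factor. Adjustment across the four factors is a different question, debated for screening designs, and is not raised here.

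**Working it through.** **1. The plan's own figure.** Inputs from section 12.2: "if 60% of families in the core navigation condition engage in mental health services"; "75% of families in any of the FN delivery conditions engage in services"; two-sided 5%; "approximately 304 participants are required to detect this effect (n=38 in each of 8 cells". Power for this outcome is not stated, so 80% is assumed. The 80% in section 12.2 refers to mediation. With the pooled-variance formula for two proportions and mean proportion 0.675:

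n per level = [1.960·√(2·0.675·0.325) + 0.842·√(0.60·0.40 + 0.75·0.25)]² / 0.15² = [1.298 + 0.550]² / 0.0225 ≈ 151.9, rounded up to 152.

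The total is 2 × 152 = 304, which matches the plan exactly, and power at 152 per level is 80.0%. Each main effect therefore compares 152 with 152 families, and the whole calculation is spent on one outcome at 5%.

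**2. Assumptions for the error rate.** The factor has no effect. Each outcome is tested once at two-sided 5%. Success on any one counts. The symptom test is independent of the access tests. None of these is stated in the plan.

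**3. Access and symptoms only** (the two called primary in the text of 4.2.1): 1 − 0.95² = 9.75%.

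**4. All three rows of Table 1.** Independence would give 1 − 0.95³ = 14.3%. That cannot apply, because 90-day receipt is time to receipt cut at day 90. The correlation of the two tests was estimated from 20,000 simulated null trials per scenario (152 v 152, exponential times, 60% or 67.5% served by day 90). P₂ is the chance that at least one of the two access tests is significant. Adding an independent symptom test gives 1 − (1 − P₂)·0.95.

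| Follow-up for time | Correlation | P₂ | 1 − (1 − P₂)·0.95 | Any of three, simulated directly |
|---|---|---|---|---|
| 90 days (Table 1) | 0.95–0.97 | 6.2–6.3% | 10.9–11.0% | 11.0–11.1% |
| 12 months (Protocol Summary) | 0.76–0.79 | 8.0–8.6% | 12.6–13.1% | 12.5–13.3% |

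The bivariate normal calculation gives 12.4–12.6% for correlations of 0.80 down to 0.76. The 13.3% is slightly high because in that run the binary test alone rejected in 5.4% of trials.

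**5. Sensitivity.** A correlation of 0.2–0.3 between the symptom test and the access tests lowers these figures by about 0.1–0.4 percentage points. Separate tests of PSC-17 and PPSC, or tests at several visits, would raise them.

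**6. Remedies compared at N=304.**

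| Approach | Error per factor | Power for access | N for 80% power |
|---|---|---|---|
| Access alone, or a fixed sequence starting with access | 5% | 80.0% | 304 |
| Bonferroni over two (0.025 each) | at most 5% | 71.1% | 370 |
| Bonferroni over three (0.0167 each) | at most 5% | 65.7% | 406 |

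**The case against.** The plan does give a lead outcome. Section 4.1 ties a meaningful contribution to access, section 3.1 fixes the 90-day definition, and section 12.2 sets the clinically important difference on the same outcome. Section 12.3 also puts the logistic model first. This is an optimization trial that feeds a later trial, so naming the deciding outcome might suffice without a gatekeeping sequence.

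Much of this stands, and it rules out several stronger readings that a reader might infer:

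- **That every primary outcome is tested at 5%.** The documents give that level once, for access. Applying it to the others is an inference, although no other level is offered.
- **That section 4.2.1 itself calls three outcomes primary.** Its text applies the word to two. Time to receipt is primary only in Table 1.
- **That the error rate is 14.3% per factor.** This needs an independence that receipt and time to receipt cannot have.
- **That components will be selected on whichever outcome is significant.** No section says so. But none excludes it, and the plural in section 3.2 leaves it open.

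What the objection does not remove is the conflict between one primary outcome in the objectives and three in Table 1. An order of modelling is also not a rule for testing. A fixed sequence is one way to settle this. Its advantage is that it costs no power on access.

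**Conclusion.** The concern holds as a conflict in the plan plus a missing success rule. The false-success chance per factor would be 9.75% for access and symptoms, about 11% for all three outcomes with time censored at 90 days, and about 12.5–13% with 12-month follow-up, against 5% for access alone. These figures depend on the assumptions in step 2 of the working. If the sponsor already intends access alone to decide, the error per factor is 5% and only the text needs correcting.

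The absence of an effectiveness model for child symptoms in section 12.3 is a gap under either reading. It should be settled before the results are analysed, because it determines what the trial can claim for each component.

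**What to change.** **Outcomes.** In sections 4.2.1 and 12.3 and in Table 1, make receipt within 90 days the single primary outcome, and state that it decides whether a component contributes meaningfully. Relabel time to receipt and child symptoms as key secondary outcomes. Within each factor test them in that order, each at two-sided 5% and only if the test before is significant. Report estimates and confidence intervals for all three whatever the test results. State the follow-up window for time to receipt.

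**Symptom model.** Name it in section 12.3. It should cover PSC-17 and PPSC according to age and use assessment times common to both arms of Factor C. Table 1 lists baseline, 3, 6, 9 and 12 months for child symptoms. Appendix A shows that schedule only for enhanced tracking, and baseline, 6 and 12 months for usual tracking. The two need to be reconciled.

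**Timing.** Record when the change was made relative to any interim data review, since the DSMB Charter schedules these every six months. Name the primary end point there too.

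**Cost.** This takes a short amendment, and it is more than rewording because the symptom model has to be written. No confirmatory symptom claim is possible for a factor that fails on access, nor, under this sequence, for one that fails on time to receipt. N=304 and the assumed 80% power for access are unchanged.
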